## **5.10 Follow-up of Adverse Events**

Any AEs will be followed up to resolution. Resolution means that the patient has returned to a Baseline state of health or the Investigator does not expect any further improvement or worsening of the AE.

## **5.11 Reporting of Serious Adverse Events to Regulatory Authorities and Investigators**

Investigators will be notified by the Sponsor or QuintilesIMS of all SAEs that require prompt submission to their IRB or IEC. Investigators should provide written documentation of IRB/IEC notification for each report to the Sponsor or QuintilesIMS. The Sponsor or QuintilesIMS will ensure that SAEs are reported to the appropriate regulatory authorities in accordance with the local regulations.

All contact details and detail instructions for SAE reporting will be provided in the site manual, and SAE form completion instruction.

## 6 STATISTICS

### 6.1 Sample Size

The PK parameters reported from a recent study with rituximab in patients with RA revealed a percentage coefficient of variation (CV%) ranging from 26.3% for  $C_{\max}$  to 37.3% for  $AUC_{0-\infty}$ .

When the evaluable sample size in each group is 84, a three group design will have 81% power to reject both the null hypothesis that the ratio of test to standard geometrics means is below 0.800, and the null hypothesis that the ratio of test to standard geometrics means is above 1.250 (i.e., that the test and standard are not equivalent), in favor of the alternative hypothesis, that the means of the two groups are equivalent, assuming that the expected ratio of means is 1.000, that data will be analyzed in the log scale using analysis of variance (ANOVA) and that each one sided test is made at the 5% level. Each of the 15 hypotheses tests (five co-primary endpoints  $\times$  three pairwise comparisons (i.e., SAIT101 vs. MabThera®, SAIT101 vs. Rituxan®, MabThera® vs. Rituxan®)) are powered at 98% to 99.0% to yield 81% study-wide power.

Approximately 282 patients (94 patients per group) will be randomized in order to yield a minimum of 84 patients per group to account for a presumed 10% withdrawal.

This 94 patients in SAIT101 group and MabThera® group will provide 96% probability of declaring the equivalence in FAS with each one sided test at the 2.5% level, accounting for a presumed 1.0 standard deviation of DAS28 from the REFLEX study, and the equivalence margin of -0.6 to 0.6 chosen as the half of a clinical meaningful improvement of 1.2 in DAS28. Considering 18% withdraw from the REFLEX study, approximately 77 patients per group will provide approximately 91% probability of declaring the equivalence in the PP set with the same above assumption.

### 6.2 Statistical Methods

Categorical variables will be summarized by the number and percentage of patients in each category. Continuous variables will be summarized using N, mean, standard deviation (SD), median, minimum, and maximum values.

For all efficacy analyses, patients will be analyzed under the treatment they were randomized to, even if the treatment actually received differs from the treatment the patient was randomized to receive. For all safety analyses, patients will be analyzed under the treatment they actually received.

Generally, the Baseline value to be used in any change from Baseline listings/summaries/graphical presentations or as a covariate in a statistical analysis is defined as the latest available pre-randomization value. If necessary, detailed Baseline definitions of specific parameters or assessments will be defined in the statistical analysis plan (SAP).

## **6.2.1 Analysis Sets**

### **6.2.1.1 Pharmacokinetic Analysis Set**

The PK analysis set will include all patients who receive both planned doses of SAIT101 or MabThera® or Rituxan®, have a measured drug serum concentration and have no major protocol deviations or violations thought to significantly affect the PK of the drug. Reasons for excluding patients from the PK Analysis set will be specified in the statistical analysis plan.

Major protocol deviations or violations thought to significantly affect the PK of the drug include (but not limited to) missing dose or incorrect dose, sampling date and time not available, sample processing errors that might render a subject's bioanalytical data to be inaccurate etc. Subjects with these issues will be reported in the study report.

### **6.2.1.2 Safety Analysis Set**

The Safety Analysis Set (SAF) will consist of all randomized patients who received at least one dose of study drug.

Safety Analysis Set will be used as the basis for all safety analyses.

### **6.2.1.3 Full Analysis Set**

The Full Analysis Set (FAS) will consist of all randomized patients in accordance with the intended treatment arm, regardless of the treatment actually received.

### **6.2.1.4 Per Protocol Set**

In this study, patients who complete at least the first course of study drug in Part A and continue study treatment up to Week 24 will be included in the PP set. A patient may be excluded from the PP set for, but not limited to, any of the following conditions:

- Patient does not meet inclusion/exclusion criteria.
- Infusion of wrong study drug occurred.

- Patient did not receive both infusions of study drug (Day 1 and Day 15).
- Intake of disallowed concomitant medication, patient to evaluation of clinical relevance of the intake.

#### **6.2.1.5 Pharmacodynamic Analysis Set**

The PD analysis set will include all patients who receive both planned doses of SAIT101 or MabThera® or Rituxan®, have at least one measured CD19+ count at scheduled time point postdose and have no major protocol deviations or violations thought to significantly affect the PD of the drug.

#### **6.2.2 Patient Disposition**

The number and percentage of patients who were screened, and were randomized will be presented. For the patients who left the study prior to randomization, a summary will be presented for the reasons of screen failure. For the patients who were randomized or re-randomized at Week 24, summaries will be presented for the number and percentage of patients who completed the study, discontinued study drug (by reason for treatment discontinuation), and withdrew early from the study (by reason for study withdrawal).

#### **6.2.3 Demographic and Baseline Characteristics Analysis**

Patient demographics and Baseline characteristics will be summarized by treatment group for all randomized patients. Continuous variables (e.g., age, weight, height, disease duration, duration of MTX use, swollen and tender joint count, patient and physician global assessments VAS, patient pain assessment VAS) will be summarized with descriptive statistics (N, mean, SD, median, minimum, maximum). Qualitative variables (e.g., gender, race, ethnicity, number of previous DMARDs) will be summarized with counts and percentages.

Relevant medical history and continuing medical conditions will be summarized by treatment group for all randomized patients.

### **6.3 Pharmacokinetic Analysis**

The PK analysis will be performed on the PK Analysis Set. The PK parameters,  $AUC_{0-t}$ ,  $AUC_{0-\infty}$ ,  $AUC_{0-d15}$ ,  $C_{max}$  after the second infusion on Day 15 and  $C_{trough}$  before the second infusion on Day 15 will be considered the primary PK endpoints. All other PK endpoints will be regarded as secondary.

The statistical analysis of the loge-transformed primary endpoints will be based on an analysis of variance model. Covariates may be added to the planned analysis. The difference in least squares means between each of the three pairs (i.e., SAIT101 vs. MabThera®, SAIT101 vs. Rituxan®, MabThera® vs. Rituxan®) and the associated 90% CI will be determined. Back transformation will provide the ratio of geometric means and 90% CI for this ratio. Equivalence will be concluded if the 90% CI for the ratio of geometric means of each of the three pairs for each primary endpoint are completely contained within the acceptance interval of 0.8 to 1.25.

Descriptive statistics (N, mean, SD, %CV, minimum, median, and maximum) will be used to summarize serum concentration data by treatment at each planned sampling time point. Concentrations that are below the lower limit of quantitation will be assigned a value of 0 for the purposes of computing descriptive statistics. Serum PK parameters calculated from the concentration-time data will also be summarized by treatment using descriptive statistics (N, mean, SD, %CV, geometric mean, geometric %CV, minimum, median, maximum).

Plots of the mean and individual serum rituximab concentrations over time for SAIT101 and MabThera® and Rituxan® will be provided following i.v. infusions.

#### **6.4 Efficacy Analysis**

The continuous efficacy endpoint will be analyzed using Analysis of Covariance (ANCOVA) using treatment (SAIT101 and MabThera®) as model factor and Baseline DAS28 as covariate. The Difference between SAIT101 and MabThera® in DAS28 change from Baseline at Week 24 and the associated two-sided 95% CI will be determined.

Equivalence will be concluded if the 95% CI for the mean difference for main efficacy endpoint is completely contained with the equivalence margin of -0.6 to 0.6. Both of the per protocol (PP) set and full analysis set (FAS) will be considered as the efficacy analysis population and the equivalence will be concluded only if the analyses of both PP set and FAS meet the equivalence criteria defined above. No missing data will be imputed for the efficacy analyses in FAS. The possibility of a treatment-by-baseline interaction may be explored as exploratory analyses. In addition, sensitivity analyses will be performed to assess the effect of missing Week 24 data and detailed in the SAP.

Binary endpoints will be analyzed as for the proportion of patients achieving an ACR20 response at Week 24. Two-sided 95% CI for the difference between SAIT101 and

MabThera® in the proportion of patients achieving an ACR20 response at Week 24 will be computed using the Wilson score method.

All statistical comparisons for the secondary efficacy variables will be made using two sided tests at the 0.05 significance level. The 95% CIs of the difference between SAIT101 and MabThera® will be computed.

All efficacy endpoints will be analyzed on the both PP set and FAS.

## **6.5 Pharmacodynamic Analysis**

A listing of PD blood sample collection times by individual, as well as derived sampling time deviations, will be provided.

Area under the depletion-time curve of CD19+ B cells depletion from time 0 across 24 weeks ( $AUC_{0-w24}$ ), depletion in CD19+ B cell count (defined as a CD19+ B cell count below  $14/\mu\text{L}$ ) will be descriptively compared between the test and comparator groups.

Observed, change from Baseline, and percent change from Baseline in CD19+ B cell counts, and depletion of CD19+ B cell counts will be summarized using descriptive statistics. Baseline is defined as the CD19+ B cell count on Day 1 (immediately before the start of the first infusion).

Observed change from Baseline in IgG, IgM, and IgA levels at Weeks 8, 16, 24, 36 and 52 and observed change from Baseline in CRP levels at Weeks 8, 16, 24, 36, and 52 will be summarized using descriptive statistics.

## **6.6 Safety Analysis**

### **6.6.1 Adverse Events**

All reported terms for AEs will be coded using the Medical Dictionary for Regulatory Activities (MedDRA). No statistical testing will be performed for AEs. Adverse events will be summarized by the number and percentage of patients experiencing events by System Organ Class (SOC), Preferred Term (PT) and severity.

A listing of all ADRs will be presented. The listing will present SOC and PT of the ADR, severity, action taken, outcome, start and stop date of the ADR, study day of onset of the ADR, age, race, and gender.

The incidence of AESI in the study will be summarized in the similar way as ADRs.

A listing will be presented for all AEs with an outcome of death. Narratives will be prepared for all patients who died.

The incidence of all SAEs will be summarized by SOC and PT, if there are a sufficient number of SAEs to warrant such a presentation. A listing of all SAEs with an onset date prior to receiving study drug will also be presented. These listings will present SOC and PT of the SAE, severity, action taken, outcome, and relationship of the SAE to study drug, start and stop date of the SAE, study day of onset of the SAE, age, race, and gender.

Narratives will be prepared for all patients with a SAE, including deaths.

Narratives will be prepared for patients who permanently discontinued from study drug due to an AE.

## **6.6.2 Clinical Laboratory Tests**

Summary statistics will be presented for observed values of all hematology, chemistry, and urinalysis parameters at each visit with laboratory assessment and at End-of-Study, and also for changes from Baseline to each post-baseline visit with laboratory assessment and End-of-Study.

Shifts (abnormal low, normal, and abnormal high) for changes from Baseline to each post-baseline visit with laboratory assessment and End-of-Study, based on normal ranges, will be presented for hematology, chemistry and urinalysis parameters.

The incidence of laboratory abnormalities overall will also be presented. Where applicable, the incidence of abnormal values will be presented separately by whether the value is abnormally high or low. Patients will be counted at most once for a high or low abnormality for each laboratory parameter.

Listings of all laboratory abnormalities will be presented (separately for hematology and blood chemistry parameters). Laboratory ranges used to identify abnormal results will be provided by the central laboratory.

Listings of observed values of all hematology, chemistry, and urinalysis parameters, as well as pregnancy test results will be presented for all randomized patients.

### **6.6.3 Concomitant Medication**

The incidence of concomitant medications will be summarized for the Safety Analysis Set by generic term coded with the World Health Organization-Drug Dictionary (WHO-DD) Enhanced, overall and by treatment group.

To allow assessment of concomitant medication that might affect the efficacy outcomes, counts will be presented for each treatment group at each visit of patients receiving any rescue medication at that visit; counts of patients receiving any rescue medication will also be presented during the study. Rescue medication is defined as the use of non-biologic DMARDs, after Week 16 of the study. Time to first incidence of rescue medication after Week 16 of the study will be estimated for each treatment group and presented using Kaplan-Meier methods. Kaplan-Meier plots will also be presented. In addition, percentiles of time without rescue medication will be presented.

### **6.6.4 Vital Signs, ECG Findings, and Physical Examination**

Summary statistics will be presented for results at each visit with vital sign assessments and at End-of-Study, as well as for change from Baseline results to each visit with vital sign assessments and End-of-Study for systolic and diastolic blood pressure, and pulse rate.

The overall incidence of vital sign abnormalities will also be presented. Patients will be counted at most once for an abnormality for each vital sign parameter.

A listing of all vital sign abnormalities will be presented for the safety set. Criteria used to define abnormal vital sign results will be defined in the SAP. Shifts (abnormal low, normal, and abnormal high) for changes from Baseline to each post-baseline visit with vital sign assessments and End-of-Study, based on normal ranges, will be presented for vital sign parameters.

A table and listing of any ECG abnormalities at Screening will be presented for the Safety Analysis Set.

A listing of physical examination abnormalities will be presented for the Safety Analysis Set.

### **6.6.5 B Cell Recovery**

B cell recovery is defined as “peripheral B cell counts that have returned to Baseline values or the lower limit of normal, whichever is lower”. The incidence of B cell recovery and CD19+ B cell count per patient will be summarized at each visit after Week 24, overall and

by treatment group. The follow-up of patients will be up to Week 52 from the start date of the first course of treatment in order to monitor B cell recovery.

### **6.7 Immunogenicity Analysis**

Incidence of HACA and neutralizing antibody and summary of counts of antibodies per patient at prior first dose on Day 1 and at Week 1, 2, 4, 12, 16, 24, 36, and 52 will be summarized overall and by treatment group.

### **6.8 Other Analysis**

The exploratory subgroup analysis will be performed. The subgroups to be used for this analysis will be based on the results of analysis of PK, PD, efficacy, safety, immunogenicity and concomitant medication.

### **6.9 Interim Analysis**

Interim analysis of 10 patients per group (30 patients in total) of safety data collected up to Week 4 and 20 patients per group (60 patients in total) of safety data collected up to Week 12 are planned. Safety data will be handled by unblinded study team in CRO for interim analysis, and the safety report will be submitted to regulatory. The study will be unblinded at Week 24 and an interim CSR will be prepared based on the 24-week data of all patients. The investigators and patients will remain blinded to treatment assignment during the post Week 24 follow-up period.

After review by DSMB, this analysis will be reported to health authorities upon request.

### **6.10 Safety Review**

An independent DSMB will be established to act in an advisory capacity to monitor patient data. The DSMB will review available study data at pre-specified time-points, as outlined in the DSMB charter.

The details of the DSMB roles and responsibilities, the stopping rules for safety reasons and the logistics of the DSMB activities will be outlined in a DSMB charter.

### **6.11 Handling of Missing Values and Outliers**

No missing data will be imputed for the efficacy analyses in FAS. Treatment of missing values, and outliers, and methodology will be detailed in a separate SAP.

## **6.12 Procedure for Reporting Deviations**

A protocol deviation is any change, divergence, or departure from the study design or procedure that is under the Investigator's responsibility and oversight (as defined by regulations) without prior written IRB/IEC approval or favorable opinion of an appropriate amendment, and that does not have a major impact on the patient's rights, safety, or well-being, or on the integrity and authenticity of the study data.

All deviations from the approved protocol must be documented and notified to the Sponsor or CRO at the earliest. The Investigator should not deviate from the protocol, except for patient safety reasons, in which case the deviation must be reported to the Sponsor or CRO immediately. The Sponsor will not assume any resulting responsibility or liability from unapproved deviations. The Investigator, according to applicable regulations and the IEC established procedures, will inform the IEC of protocol deviations.

All instances where the requirements of the study protocol are not complied with will be captured in the clinical trial management system (CTMS) and the study monitor will prepare a Protocol Deviation/Violation Log. Corresponding patients may be discontinued from the study treatment at the discretion of the Sponsor/designee. Deviations from the study protocol should not be made other than as part of a protocol amendment. An amendment must be agreed upon by the Sponsor, but not implemented until written IRB/IEC approval is obtained, except where necessary to eliminate an immediate hazard to study patients or when the change(s) involves only logistical or administrative aspects. Protocol deviations/violations and the reason why they occurred will be documented in the clinical study report (CSR).

## **7 MANAGEMENT OF THE INVESTIGATIONAL MEDICINAL PRODUCT**

### **7.1 Investigational Medicinal Product Identification**

SAIT101, Rituxan® and MabThera® will be provided in sterile, preservative-free, non-pyrogenic, single-use vials containing 500 mg of rituximab per 50 mL. Two vials will be used per infusion (1,000 mg per 100 mL) with each carton of study drug containing two 50 mL vials of either SAIT101, Rituxan® or MabThera®.

The SAIT101, Rituxan® and MabThera® vials will be different in size. Therefore, site staff managing medication preparation will be unblinded.

### **7.2 Packaging and Labeling**

Each carton and medication vial will be labelled with all the required information according to local regulations, including the Protocol Number (AGB001) and a unique identifier (Med ID) in a blinded manner. This will be programmed into the IXRS. At each infusion visit, the IXRS will assign the correct vial for the allocated treatment group and visit and the Med ID will be linked to an individual patient. The Med ID is assigned by the IXRS.

Any used and unused product or waste material should be disposed of in accordance with local requirements, when certificates of destruction are available, or in case not possible, centrally as per Sponsor guidance.

### **7.3 Storage**

Study drugs will be stored in a secure area according to local regulations. Access should be strictly limited to unblinded study personnel (e.g., pharmacist). It is the responsibility of the Investigator, Sub-investigator, or authorized person to ensure that study drugs are only administered to study patients.

All study drugs must be kept in a secure place under appropriate storage conditions. The medication vials must be stored in a refrigerator at a controlled temperature (2 to 8°C) and handled according to GCP. Vials should be kept in the outer carton in order to protect it from light. A temperature log must be kept, on which the storage temperature of the study drug is recorded at least once a day. The study drug, SAIT101, Rituxan® and MabThera®, must be kept strictly separate and in a different location than commercially available product at all times. Additional details regarding the storage and handling of the study drugs will be provided to the study centers.

## **7.4 Preparation, Storage after Preparation and Administration**

Study drug preparation should be done using aseptic techniques. Sterile, non-pyrogenic, disposable containers, syringes, needles, stopcocks, and transfer tubing, etc., should be used during dosage preparation and infusion.

An unblinded study team member should dilute the 2 vials of study drug (1,000 mg) assigned via IXRS to a calculated concentration of 1 to 4 mg/mL rituximab in a 250 mL, 500 mL or 1,000 mL polyvinyl chloride (PVC) or polyethylene (PE) infusion bag containing either 0.9% sodium chloride or 5% glucose for injection. The unblinded study team member should clearly label the bag in a blinded manner with the study code and patient number and total dose of rituximab contained in the bag.

The prepared infusion solutions of study drug are physically and chemically stable for 24 hours at 2 to 8°C and subsequently 12 hours at room temperature. From a microbiological point of view, the prepared infusion solutions should be used immediately. If not used immediately, the prepared infusion solutions must be stored at 2 to 8°C for no longer than 24 hours. The prepared infusion solutions must be at room temperature prior to infusion.

Infusion of the study drug should be performed according to the recommended infusion rates provided in Table 1.

An infusion device capable of administering the study drug with rates varying from as low as 0.2 mL/minute up to 3.3 mL/minute would be suitable. This would be best achieved by a volumetric infusion pump. An in-line filter is not mandatory.

More detailed instructions for study drug preparation, storage, and infusion will be provided in the Pharmacy Manual.

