## **3.2 Treatments**

### **3.2.1 Test Product and Comparator, Dose and Mode of Administration**

SAIT101 is a sterile, clear to opalescent and colorless or a pale yellow, preservative-free solution for i.v. infusion. The formulation of SAIT101 is similar to MabThera® or Rituxan®.

Each patient will be randomized on Day 1 to receive one of three possible treatments (study drug):

- SAIT101: 1,000 mg (10 mg/mL)-Test product;
- Rituxan®: 1,000 mg (10 mg/mL)-Comparator;
- MabThera®: 1,000 mg (10 mg/mL)-Comparator.

All patients received premedication with 100 mg i.v. methylprednisolone (or its equivalent), an antipyretic and an antihistaminic (e.g. acetaminophen and diphenhydramine) per the accepted infusion protocols for rituximab prior to study drug infusions to decrease incidence rate and severity of acute infusion-related reactions.

Since hypotension may occur during rituximab infusion, consideration should be given to withholding anti-hypertensive medications 12 hours prior to the infusion.

The Day 1 infusion rate (both week 0 and week 24) of SAIT101 or MabThera® or Rituxan® will start at 50 mg/hour; after the first 30 minutes, it can be escalated in 50 mg/hour increments every 30 minutes, to a maximum of 400 mg/hour. If there has been no infusion related reaction on Day 1, the Day 15 infusion (both first and second courses) can be infused at 100 mg/hour and increased by 100 mg/hour increments at 30 minute intervals, to a maximum of 400 mg/hour.

The recommended infusion rates are presented in Table 1.

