**Table 1 Recommended Infusion Rates**

Day 1 infusion	Total dose (mg)	Time (minutes)***	Day 15 infusion	Total dose (mg)	Time (minutes)***
50 mg/h	25	0-30	100 mg/h	50	0-30
100 mg/h	50	31-60	200 mg/h	100	31-60
150 mg/h	75	61-90	300 mg/h	150	61-90
200 mg/h	100	91-120	400 mg/h	700	91-196**
250 mg/h	125	121-150	-	-	-
300 mg/h	150	151-180	-	-	-
350 mg/h	175	181-210	-	-	-
400 mg/h	200	211-240	-	-	-
400 mg/h	100	241-255*			

\* Approximately at 255 minutes (4 hours 15 minutes) to complete the 1,000 mg total dose.

\*\* Approximately at 196 minutes (3 hours 16 minutes) to complete the 1,000 mg total dose.

\*\*\*Allowed window for infusion rate time: For each time point:  $\pm 5$  minutes (e.g. when start 50 mg/h for first course: 25~35 minutes can be allowed).

In the event that a patient experiences an infusion-related reaction or an adverse drug reaction (ADR), the infusion rate should be reduced to half the rate (e.g., from 100 mg/hour to 50 mg/hour). Once the infusion-related reaction or ADR has resolved, the Investigator should wait an additional 30 minutes while delivering the infusion at the reduced rate. If tolerated, the rate may be increased to the next closest rate on the patient's infusion schedule. Please refer to the following examples:

**(Example 1)** An infusion-related reaction or an ADR at a rate of 50 mg/h  $\rightarrow$  change rate to 25 mg/h  $\rightarrow$  reaction resolved  $\rightarrow$  additional 30 minutes at a rate of 25 mg/h  $\rightarrow$  change back to 50 mg/h.

**(Example 2)** An infusion-related reaction or an ADR at a rate of 300 mg/h → change rate to 150 mg/h → reaction resolved → additional 30 minutes at a rate of 150 mg/h → change back to 200 mg/h.

Drug infusions will take place under the close supervision of an experienced physician, and in an environment where full resuscitation facilities are immediately available. Although the study drug may be administered on an outpatient basis, patients may be hospitalized for observation at the discretion of the Investigator, and such instances of planned hospitalization will NOT be recorded as a serious adverse event (SAE).

Any drugs that are used to manage hypersensitivity reactions or ADRs, including but not limited to epinephrine, antihistamine, and corticosteroid, should be immediately available in case of emergency.

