Attention should be given to the development of anaphylaxis during infusion of the study drug. When an anaphylactic reaction is suspected during infusion of the study drug:

- Discontinue the study drug.
- Apply a tourniquet close to the infusion site in order to slow systemic absorption of the study drug. Do not block artery flow.
- Perform appropriate airway management.
- If required, administer antihistamine, epinephrine, or other drugs.
- Closely monitor the patient and document the observations.

Patients who experience a moderate to severe infusion-related reaction (fever, chills or hypotension), should have their infusion interrupted immediately and should receive aggressive symptomatic treatment, such as glucocorticoids, epinephrine, bronchodilators or oxygen, as per local practice. Depending on the severity of the infusion reaction and the required interventions, patients should either have their infusion temporarily interrupted or be discontinued from the study treatment. The infusion should not be restarted before all the symptoms have disappeared, and then it should be restarted at half the rate. If the patient tolerates the reduced rate for 30 minutes then the infusion rate may be increased to the next closest rate on the patient's infusion schedule. If the subject does not tolerate the reduced rate for at least 30 minutes or, if the same severe (NCI-CTCAE Grade 3) infusion reaction occurs for a second time, the patient can be discontinued from the study treatment.

At the end of each infusion, the i.v. line is recommended to remain in place for at least 1 hour to allow infusion of i.v. drugs if necessary. If no AE occurs during this time, the i.v. line may be removed.

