#### **Second Infusion (Day 15 of First Course)**

Patients who experienced infusion-related reactions to the first infusion should receive study drug as per the initial infusion schedule, with the rate of infusion not exceeding half that associated with the prior reactions. If this reduced rate is tolerated for 30 minutes, then the infusion rate may be increased to the next closest rate following the infusion schedule.

Patients who miss the allocated day (Day 15  $\pm$  1 day) for the second infusion (the first infusion will be administered following randomization on Day 1) will be contacted and another visit arranged as soon as practically possible in order to administer study drug. Such cases will be considered protocol deviations (see Section 3.13).

If a patient experiences a new infection or other AE between the Day 1 and Day 15 infusions of any treatment, the Day 15 infusion should be delayed until the infection or AE has completely resolved and the Investigator considers it safe to resume treatment. A maximum delay of 15 days from the scheduled date of the second infusion is permitted. Patients who have a delay of >15 days in receiving the second infusion due to an AE or otherwise will be discontinued from the study treatment.

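### The infusion-device range called suitable (0.2 to 3.3 mL/min) does not cover every permitted bag and rate: it fails at 250 mg/h and above from the 1,000 mL bag, and at the 25 mg/h post-reaction rate from the 250 mL bag.

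*Protocol*

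**What the plan says.** In Section 7.4 an unblinded team member makes up the contents of two vials, 1,000 mg in all, and the dilution is "to a calculated concentration of 1 to 4 mg/mL rituximab in a 250 mL, 500 mL or 1,000 mL" bag. No bag size is tied to particular infusion rates. The same section directs infusion at the Table 1 rates and describes a device "with rates varying from as low as 0.2 mL/minute up to 3.3 mL/minute would be suitable". Further detail is left to the Pharmacy Manual.

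Section 3.2.1 starts the Day 1 infusion at 50 mg/h, after which "it can be escalated in 50 mg/hour increments every 30 minutes, to a maximum of 400 mg/hour". Day 15 runs at 100, 200, 300 and 400 mg/h if Day 1 passed without a reaction.

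Three rules halve the rate after a reaction:

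- Section 3.2.1, Example 1 after Table 1: a reaction at 50 mg/h leads to 25 mg/h and, once it resolves, an "additional 30 minutes at a rate of 25 mg/h".
- Section 3.2.1, moderate to severe reactions: the infusion is interrupted until symptoms have gone, "and then it should be restarted at half the rate".
- Section 3.2.2, Day 15: a patient who reacted on Day 1 is infused "with the rate of infusion not exceeding half that associated with the prior reactions".

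**The concern.** Rates are prescribed in mg/h, but a pump is set by volume. Whether a given device can deliver a given rate therefore depends on the bag, and Section 7.4 gives one device range for bags whose concentrations differ fourfold. A site would reasonably read the sentence as saying that any permitted bag works with such a device.

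The low end matters more. The Day 1 schedule starts every patient at 50 mg/h, and the protocol names 25 mg/h as the response to a reaction there. Infusion reactions are an adverse event of special interest in this trial (Section 5.4). If the pump cannot go that low, stopping first does not solve the problem, because the restart is also at half rate. At the high end the consequence is a longer infusion and departure from Table 1.

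**Working it through.** **Inputs.** Dose 1,000 mg; bags of 250, 500 and 1,000 mL; device range 0.2 to 3.3 mL/min (all Section 7.4). Scheduled rates 50 to 400 mg/h (Table 1). Lowest post-reaction rate 25 mg/h (Example 1).

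**Assumption.** The final volume equals the bag size, as the 1 to 4 mg/mL limits imply: 1,000/250 = 4, 1,000/500 = 2 and 1,000/1,000 = 1 mg/mL.

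**Formula.** Flow (mL/min) = rate (mg/h) ÷ concentration (mg/mL) ÷ 60.

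**The plan's own figures.** The protocol does not say how they were obtained. The upper limit matches 400 mg/h at 2 mg/mL: 400/2/60 = 3.33. The lower limit matches either 50 mg/h at 4 mg/mL (50/4/60 = 0.208) or 25 mg/h at 2 mg/mL (25/2/60 = 0.208). The 1,000 mL bag at its upper steps, and the 250 mL bag at 25 mg/h, are not reflected in either limit.

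**All permitted bags (mL/min; bold = outside 0.2 to 3.3 after rounding to one decimal).**

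| Rate (mg/h) | 250 mL, 4 mg/mL | 500 mL, 2 mg/mL | 1,000 mL, 1 mg/mL |
|---|---|---|---|
| 25 | **0.104** | 0.208 | 0.417 |
| 50 | 0.208 | 0.417 | 0.833 |
| 200 | 0.833 | 1.667 | 3.333 |
| 250 | 1.042 | 2.083 | **4.167** |
| 300 | 1.250 | 2.500 | **5.000** |
| 350 | 1.458 | 2.917 | **5.833** |
| 400 | 1.667 | 3.333 | **6.667** |

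**What a pump limited to the stated range could deliver.** Lowest rate from the 250 mL bag: 0.2 × 60 × 4 = 48 mg/h, where 25 mg/h is required. Highest rate from the 1,000 mL bag: 3.3 × 60 × 1 = 198 mg/h.

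**Share of the dose scheduled above 200 mg/h (Table 1).** Day 1: 125 + 150 + 175 + 200 + 100 = 750 of 1,000 mg. Day 15: 150 + 700 = 850 of 1,000 mg.

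**Infusion time from the 1,000 mL bag if held at 200 mg/h (3.33 mL/min).** Day 1: 250 mg in the first 120 minutes, then 750/200 × 60 = 225 minutes, total 345 against 255 in Table 1. Day 15: 150 mg in the first 60 minutes, then 850/200 × 60 = 255 minutes, total 315 against 196.

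**If the assumption fails.** Section 7.1 gives the drug volume as 100 mL. Added without withdrawing diluent, it makes 350 or 600 mL in the two smaller bags, at 2.86 or 1.67 mg/mL. Then 25 mg/h from the 250 mL bag needs 0.146 mL/min, still too low. From the 500 mL bag, 350 and 400 mg/h need 3.5 and 4.0 mL/min, so that bag fails too. The 1,000 mL bag would be at 0.91 mg/mL, below the permitted 1 mg/mL, so that case is not counted.

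**The case against.** The sentence describes a capability and sets no ceiling. It does not exclude a wider-range pump, and nothing shows that any site has one confined to these limits. The Pharmacy Manual may resolve the matter. Both points stand, and they limit the practical weight.

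The high end is the softer half. Table 1 rates are headed as recommended, escalation is permissive, and a slower infusion still gives the full dose. That is fair, although Section 7.4 does direct use of Table 1.

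The low end needs three things together: a reaction at the 50 mg/h step, a 250 mL bag, and a pump that cannot run below 0.2 mL/min. A reaction at 100 mg/h halves to 50 mg/h, which is inside the range (0.208 mL/min). For the Day 15 rule the earlier reaction is known before the bag is prepared, so the pharmacy could choose 500 mL. For moderate to severe reactions, Section 3.2.1 also allows treatment to be discontinued. What remains is chiefly a reaction at 50 mg/h with a 250 mL bag already running. That gap is narrow, but it falls on a rate the protocol prescribes by name.

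None of this makes the stated range adequate for the bags and rates the protocol permits.

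**Conclusion.** The stated range is wrong as written. Covering every permitted bag and rate takes about 0.10 to 6.7 mL/min, so the lower limit is about twice what it should be and the upper limit about half. The 250 mL bag is adequate for every scheduled Table 1 rate and fails only at 25 mg/h. The 1,000 mL bag fails from 250 mg/h upward. The 500 mL bag is adequate to rounding.

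The arithmetic rests on final volume equalling bag size; the alternative of adding 100 mL does not remove the mismatch. Any effect on patients or visits depends on a pump limited to the stated range and on what the Pharmacy Manual says, neither of which can be seen here. The error should be corrected, but its practical effect is likely small, and no statistical conclusion depends on it.

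**What to change.** Preferred: change the Section 7.4 sentence to a device range of about 0.10 to 6.7 mL/min, which covers 25 mg/h at 4 mg/mL (0.104) through 400 mg/h at 1 mg/mL (6.67). All three bags stay available.

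Two alternatives restrict preparation instead:

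- Drop the 1,000 mL bag and state 0.1 to 3.3 mL/min.
- Keep 0.2 to 3.3 mL/min and limit preparation to 2 mg/mL in a 500 mL final volume. This removes two of the three bag sizes and is more than the problem requires.

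Under any option, say that the bag size is the final volume and use the same wording in the Pharmacy Manual. The cost is one or two sentences in Section 7.4 and the matching manual text, with no change to design, sample size or analysis.
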